Title: Randomized COmparison of Isolated Radial Artery ComPrEssioN versus Radial and Ipsilateral Ulnar Artery Compression in Achieving Radial Artery Patency: OPEN-Radial Trial

NCT Number: NCT04002791

Date: March 1, 2019

STUDY PROTOCOL AND STATISTICAL ANALYSIS PLAN

The study was conducted at a tertiary care center in India. The protocol was reviewed and approved by the local institutional review board.

Inclusion criteria: Patients referred for cardiac catheterization using TRA.

- Exclusion criteria: 1: Patients with a history of previous ipsilateral TRA.
 - 2: Warfarin anticoagulated patients or patients on novel oral anticoagulant compounds.
 - 3: Patients requiring continuous intravenous heparin infusion for any indication.
 - 4: Presence of plethysmographic waveform when both radial and ulnar arteries were occlusively compressed (suggestive of presumed interosseous artery related digital plethysmographic waveform).
 - 5: Absence of palpable ulnar pulse.
 - 6: Lack of informed consent.

Primary study endpoints:

The primary study endpoint was achievement of patent hemostasis, defined as presence of radial artery patency at 15 minutes after onset of hemostatic compression of radial artery, using plethysmographic technique as described below.

Secondary study endpoint:

The secondary study endpoint was RAO evaluated by plethysmographic technique, 1hour after the removal of hemostatic compression device was the secondary study endpoint.

All patients underwent Barbeau's test before the procedure, although TRA was performed if inclusion criteria were met. Reverse Barbeau test was also performed before the procedure, when the ipsilateral ulnar artery was transiently compressed in conjunction with radial artery compression, while plethysmographic waveform monitoring was in progress with the sensor placed on ipsilateral index finger. Total absence of waveform while both arteries were compressed was necessary for inclusion into the trial. Upon release of the radial artery, return of the waveform was considered evidence of patency of radial artery at baseline. Randomization scheme is depicted in the CONSORT diagram shown in Figure 1. Patients randomized to Group 1 received hemostasis post-procedure using TR Band (Terumo Interventional Systems, Japan), and Group 2, using VASOBand (VASOInnovations Inc., Los Angeles, California, USA).

Transradial Procedure:

The patients underwent standard preparation with infiltration of lidocaine using a 25gauge short needle at the distal forearm in the vicinity of the radial pulse, 2 to 3 finger breadths above the wrist joint. Using a micropuncture system and counter-puncture technique,¹¹ a 5-French hydrophilic-coated 7 cm introducer sheath (RadiofocusTM, Terumo, Japan) was placed in the radial artery. A vasodilator cocktail containing of 200 µg of nitroglycerin and 2.5 mg of verapamil was administered intra-arterially via the introducer. 5000 U bolus of unfractionated heparin was administered intravenously after placement of the sheath. The remainder of the procedure was completed following the standard routine with coronary angiography performed using catheters deemed necessary by the primary operator.

Hemostasis protocol:

Group 1: Patients randomized to Group 1 received hemostatic compression using TR Band. The band was applied by placing the green centering marker 2 to 3 mm proximal to the skin entry site, at the presumed arteriotomy site, and after securing the band around the forearm circumferentially using Velcro, the inflatable bladder was inflated using air in a standard fashion. The introducer sheath was then gently removed and the inflated bladder was gently deflated to the point where a small amount of bleeding was noted at the skin puncture site, at which point the bladder was re-inflated to achieve dry hemostasis using the lowest necessary amount of air injected into the bladder. The care team was allowed adjustment in hemostatic pressure throughout the hemostatic compression period and followed the patent hemostasis protocol. The band was left in place for a minimum duration of 120 minutes. After 120 minutes, the band bladder was gradually deflated over 15 minutes and the band was removed if there was no bleeding. Inadequate hemostasis was treated with hemostatic pressure adjustment at any time during the hemostatic process. If rebound bleeding occurred, the band was re-inflated and hemostatic compression was reapplied for 30 minutes after which the weaning process was repeated, and the band was removed.

Group 2: Patients randomized to Group 2 received hemostatic compression using VASOBand. VASOBand was placed on the forearm, with the distal edge of the band aligned with the crease of the wrist and the band was secured circumferentially around the forearm using Velcro. Ulnar balloon was inflated using 15 ml of air. Radial balloon was inflated using 15 to 20 ml of air, the introducer sheath was removed, and the radial bladder was then deflated to observe a small amount of bleeding at the skin puncture site, after which it was inflated with the smallest necessary volume of air to achieve dry hemostasis. Ulnar balloon was deflated after 60 minutes of onset of compression by the care team. At this point, hemostatic pressure adjustment was allowed if deemed necessary by the care team. No other adjustments in hemostatic pressure were made. After 120 minutes, as per the institution's protocol, the band compression pressure was weaned over 15 minutes and the band was removed. If rebound bleeding occurred, the band was re-inflated and hemostatic compression was reapplied for 30 minutes after which the weaning process was repeated, and the band was removed. A dry dressing was applied with minimal pressure at the puncture site to cover the dermotomy. Inadequate hemostasis was treated with hemostatic pressure adjustment at any time during the hemostatic process.

Evaluation of radial artery patency:

In Group 1 patients, radial artery patency was evaluated by performing reverse Barbeau test. Ipsilateral ulnar artery at the distal forearm, and the radial artery proximal to the band were occlusively compressed while observing the plethysmographic waveform with a plethysmograph sensor placed on the ipsilateral index finger. Absence of waveform was noted. Then while transiently maintaining ulnar artery occlusive compression, radial artery was released. Presence of plethysmographic waveform was considered evidence of radial artery patency.

In Group 2 patients, the plethysmographic sensor was placed on the ipsilateral index finger. Absence of waveform was considered evidence of radial artery occlusion. If waveform was present, the radial artery was compressed proximal to the band, in the mid-forearm, with adequate compression to eliminate the palpable pulse at that point. Absence of a plethysmographic waveform at this time confirmed occlusive ipsilateral ulnar artery compression. Upon release of radial artery compression proximal to the band in the mid-forearm region, return of plethysmographic waveform was considered evidence of radial artery patency with presence of antegrade flow.

A separate team evaluated radial artery patency after the application of the band, and at 15 minutes, 60 minutes, 90 minutes and 120 minutes after band application. If the band compression exceeded 120 minutes, patency was evaluated at 30-minute intervals after 120 minutes. Radial artery patency was evaluated at the time of discharge, at a minimum of 60 minutes after the band was removed and the dressing was applied. Findings of radial artery patency obtained by the monitoring team were blinded from the clinical care team. The care team performed their own patency evaluation following the local "patent hemostasis" routine after onset of hemostatic compression. All equivocal plethysmographic tests were evaluated by performing radial artery duplex Doppler ultrasonography.

Demographic, laboratory, as well as procedural variables were recorded upon enrollment. Post procedural variables including systolic blood pressure, diastolic blood pressure, presence of pain at the forearm, and difficulty in hardware transit during the procedure suggestive of spasm, and occurrence of hand pain throughout the procedural and post-procedural predischarge course were also recorded.

Statistical Analysis:

Categorical variables were expressed as proportions, and differences between the two groups were assessed using Chi-square test, or Pearson test as deemed appropriate. Numeric variables were assessed for normality of the distribution and were expressed as mean and standard deviation for normally distributed variables, and median as well as interquartile range for those without normal distribution. Parametric tests were used to compare differences between the two groups for normally distributed numeric variables, and nonparametric tests were used in those variables with a non-normal distribution. Paired t-test was performed to compare serial blood pressure observations. Binary logistic regression was performed to identify independent predictors of RAO. Mediation analysis was performed to identify potential mechanistic basis of the effect observed in the treatment (VASOBand) group.

Sample Size Calculation:

Based on the available literature, using the current standard of care TR Band, sample size was calculated for our primary study endpoint, achievement of patent hemostasis as defined above. We used an optimistic 80% patent hemostasis rate in the TR Band group in view of the high level of training of the research site in preventing RAO. The only published randomized trial using prophylactic ipsilateral ulnar artery compression during radial artery hemostatic compression has shown 96% achievement of patent hemostasis at 15 minutes after onset of compression. Using 80% rate of patent hemostasis in single-balloon band (TR Band) group and 95% rate of patent hemostasis in the dual-balloon band (VASOBand) group, a Chi-square model provided a sample size of 194 patients equally divided between two groups, necessary to achieve a 90% power with an alpha error of .05. Average incidence of RAO 1-hour after removal of

hemostatic compression device, using the findings from recent trials reporting RAO rates at < 24 hours sampling^{5,9,12} was expected to occur in 11% of patients in TR-Band group and 1.5% in the experimental group, providing a sample size of a total of 250 patients in order to have a 90% chance of detecting a difference in the secondary end-point of RAO with an alpha=.05. It is important to note that RAO incidence is very dependent on time of evaluation after the procedure, data from recent studies mentioning the time point of RAO evaluation were used for sample size calculation. SPSS 26 (IBM Corporation, Armonk, NY) statistical software was used for the analyses.

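### The hand-pain window opens before either band is applied and no split at band application is planned, so procedural pain common to both arms could dilute the device comparison

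*Combined protocol and SAP*

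**What the plan says.** All references are to the combined protocol and SAP.

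- **Recording window.** The last paragraph under Evaluation of radial artery patency lists the variables collected. For hand pain it reads: "occurrence of hand pain throughout the procedural and post-procedural predischarge course were also recorded". It gives no assessment times, severity scale or pre-band baseline.
- **Forearm pain.** The same paragraph lists it separately: "Post procedural variables including systolic blood pressure, diastolic blood pressure, presence of pain at the forearm". It is labelled post-procedural, but no start time is stated. Difficult hardware transit suggesting spasm is a further separate item.
- **Start of the randomized exposure.** The paragraph on randomization says: "Patients randomized to Group 1 received hemostasis post-procedure using TR Band". The same holds for VASOBand in Group 2. Transradial Procedure describes one puncture, sheath and catheter sequence for everyone.
- **Exposure specific to Group 2.** Under Hemostasis protocol: "Ulnar balloon was inflated using 15 ml of air", and later "Ulnar balloon was deflated after 60 minutes of onset of compression by the care team".
- **Analysis.** Statistical Analysis has one rule for categorical variables: "differences between the two groups were assessed using Chi-square test, or Pearson test as deemed appropriate". Hand pain gets no rule of its own.
- **Status.** The primary endpoint is patent hemostasis at 15 minutes and the secondary is RAO one hour after band removal. Hand pain is neither.

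**The concern.** The arms are treated alike until the band is applied, so only pain that starts or worsens after that moment can differ because of the device. A yes/no variable that opens with the catheterization also counts patients whose pain came from the procedure. Such a patient is already a yes, and new or worse pain under the band changes nothing in the table.

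Forearm pain and hand pain are the only patient-felt variables the plan names. Group 2 alone has the ulnar artery compressed by a balloon for the first 60 minutes, so hand pain is a natural place to look for a tolerability cost. At stake is the reading of a null hand-pain comparison. Printed beside a patency benefit, it could be taken as reassurance about the dual-balloon band when the variable was poorly placed to show a difference.

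The plan does tie its patency checks to band application (15, 60, 90 and 120 minutes). It does not do so for hand pain.

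**Working it through.** **1. The plan's own figure.** No figure is given for pain, so the primary sample size serves to fix the conventions. Inputs from Sample Size Calculation are 80% vs 95%, 90% power and alpha .05. With a two-sided test and unpooled variance:

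n per arm = (1.960 + 1.282)² × (0.80×0.20 + 0.95×0.05) / 0.15² = 10.507 × 0.2075 / 0.0225 = 96.9, so 97 per arm and 194 in total.

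This matches the stated 194. I therefore use two-sided alpha .05 with 97 per arm, and also 125 per arm from the total of 250 given for RAO. The equal split of the 250 is my assumption.

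**2. Formula for dilution.** Let q be the risk of procedural hand pain, the same in both arms because the bands are not yet on. Let b₁ and b₂ be the band-phase risks under TR Band and VASOBand. If the two kinds of pain are independent within a patient:

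- whole-window risk in arm i: pᵢ = 1 − (1 − q)(1 − bᵢ)
- risk difference: p₂ − p₁ = (1 − q)(b₂ − b₁)

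Any q above zero shrinks the difference by the factor (1 − q), moves the risk ratio towards 1, and lowers power in every case computed below.

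**3. Illustration.** The documents give no value for q, b₁ or b₂; all are assumptions. Take b₁ = 3% and b₂ = 12%. For example, at q = 10%: p₁ = 1 − 0.90×0.97 = 12.7%, p₂ = 1 − 0.90×0.88 = 20.8%, and the difference is 0.90 × 9 = 8.1 points. Power is the exact unconditional power of the uncorrected chi-square test.

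| q | TR Band vs VASOBand, whole window | Difference (points) | Risk ratio | Power, 125 per arm | Power, 97 per arm |
|---|---|---|---|---|---|
| 0% | 3.0% vs 12.0% | 9.0 | 4.0 | 80% | 69% |
| 2% | 4.9% vs 13.8% | 8.8 | 2.8 | 69% | 58% |
| 5% | 7.85% vs 16.4% | 8.55 | 2.1 | 55% | 45% |
| 10% | 12.7% vs 20.8% | 8.1 | 1.6 | 40% | 33% |
| 20% | 22.4% vs 29.6% | 7.2 | 1.3 | 25% | 21% |

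The difference itself shrinks only modestly. Most of the power is lost because the shared background raises the variance.

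**4. Sensitivity to the assumed band effect, 125 per arm.**

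- 5% vs 30%: power is 99% at q = 10% and 92% at q = 20%, so little is lost.
- 5% vs 20% (normal approximation): power falls from 95% at q = 0 to 54% at q = 20%.
- 3% vs 6%: power is only about 20% even at q = 0, so a split would not rescue the comparison.

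**The case against.** The case on the other side has five parts.

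- **Hand pain is not an endpoint.** It is one item in a list of recorded variables, with no tolerability hypothesis or sample size attached, and its test is only the generic rule. This stands and sets the weight of the point.
- **Procedural pain may seldom be hand pain.** Puncture is at the distal forearm under lidocaine, vasodilators are given through the sheath, and forearm pain and suspected spasm are separate items. The rate q could be near zero: at 3% vs 12% and 125 per arm, q = 1% still leaves 74% power. This stands as a limit on size. It does not remove the problem, because the plan itself extends the hand-pain window into the procedure.
- **Onset times may have been kept.** A reader might infer that pre-band and post-band pain were recorded as a single yes/no flag. The text does not say so, and no case report form is included. What can be said is that no split is planned.
- **The effect is assumed.** A reader might infer that a real excess would probably be reported as no difference. That depends wholly on the assumed rates, as the sensitivity cases show. The text supports only that it could be.
- **Forearm pain is already labelled post-procedural.** This stands. It needs only a stated start time.

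**Conclusion.** The point holds as a minor one, worth acting on because the remedy is cheap. The stated hand-pain window includes time before either band is on, and no analysis is planned that separates it. If whole-window occurrence is compared between arms, procedural pain dilutes any difference due to the band.

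Given that comparison, the direction follows for any procedural rate above zero under independence. The size cannot be fixed from the documents. In the 3% vs 12% illustration at 125 per arm, power runs from 80% with no procedural pain to 25% at a 20% rate; with a band effect of 5% vs 30% the loss is small. These figures rest on assumed pain rates, independence of the two sources, a two-sided test at .05 and equal arms.

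A reader might be tempted to extend this to the trial's main findings. The documents do not support that: patency at 15 minutes and RAO after band removal are measured separately, and neither uses the pain variable.

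**What to change.** 1. On the case report form, record whether hand pain began before or after band application, ideally with time of onset, and whether pain already present worsened under the band. If onset times are already in the records, no new field is needed for onset.
2. Add one sentence to Statistical Analysis: the arms are compared on hand pain that starts or worsens from band application to discharge, and hand pain before band application is reported by arm as a baseline characteristic.
3. For forearm pain, confirm that its window starts at band application.

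If timing was not kept and cannot be recovered, report hand pain descriptively, and state that the window includes the procedure and that a null result is weak evidence on tolerability.

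The cost is about one form field, one SAP sentence and slightly more bedside recording. No treatment, endpoint or sample size changes. The split removes the dilution but does not give adequate power for a small band effect.

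### The RAO predictor model is ordinary logistic regression on about 16 expected events (12 at N=194), with no provision for a predictor that has no events; if randomised arm is a term, its odds ratio is not finite in about 15% of trials at N=250

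*Combined protocol and SAP*

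**What the plan says.** The combined protocol and SAP gives this model one sentence, under Statistical Analysis: "Binary logistic regression was performed to identify independent predictors of RAO". It does not list the terms, say whether randomised arm is among them, limit their number, name the test by which a predictor is judged, or say what is done when a predictor has no events.

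Other sections supply the context:

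- **Direct comparison.** For categorical variables, "differences between the two groups were assessed using Chi-square test, or Pearson test as deemed appropriate". RAO one hour after device removal is the secondary endpoint, so this test covers it.
- **Expected rates.** Under Sample Size Calculation, RAO "was expected to occur in 11% of patients in TR-Band group and 1.5% in the experimental group".
- **Sample size.** For RAO the plan gives this figure: "providing a sample size of a total of 250 patients". For patent hemostasis, "a Chi-square model provided a sample size of 194 patients equally divided between two groups". It does not say which was the enrolment target.
- **Candidate predictors.** At the end of Evaluation of radial artery patency: "Demographic, laboratory, as well as procedural variables were recorded upon enrollment". Post-procedural items are added, including "presence of pain at the forearm, and difficulty in hardware transit during the procedure suggestive of spasm, and occurrence of hand pain".
- **Software.** "SPSS 26 (IBM Corporation, Armonk, NY) statistical software was used for the analyses".

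**The concern.** Ordinary logistic regression estimates by maximum likelihood. If a yes/no term has no RAO at one of its levels, the likelihood keeps rising as the coefficient moves toward infinity. The odds ratio and its Wald interval are then not finite. Software may print a very large coefficient with an enormous standard error, and the Wald p-value is close to 1.

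The plan expects few events, and very few in the VASOBand arm, so this outcome is not remote. For the arm term it occurs exactly when VASOBand has done best. It can also occur without an arm term, because several recorded variables are yes/no items that may be uncommon.

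What is at stake is the stated purpose of the model, which is to name independent predictors. In an affected trial it gives no usable odds ratio or interval for that term. If predictors are judged by Wald p-values, arm cannot be named at all.

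**Working it through.** **Inputs.** RAO rates of 11% and 1.5%; N=250 and N=194 (all from Sample Size Calculation). Equal allocation is stated for 194 and assumed for 250, giving 97 and 125 per arm. Two-sided alpha of .05 and no missing RAO data are assumed.

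**The plan's sample sizes.** For 80% versus 95% at 90% power, the unpooled formula gives (0.8×0.2 + 0.95×0.05) × (1.960 + 1.282)² / 0.15² = 96.9, so 97 per arm and 194 in total, as stated. For RAO the answer depends on the formula: pooled 270, unpooled 264, likelihood-ratio 244. Exact power of the uncorrected chi-square test at 125 per arm is 91.9%. The figure of 250 is therefore acceptable and is not in dispute.

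**Expected events**, n × (0.11 + 0.015):
- N=250: 13.75 + 1.875 = 15.6
- N=194: 10.67 + 1.455 = 12.1

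**No RAO in the VASOBand arm**, (1 − p)ⁿ:

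| True VASOBand rate | N=250 | N=194 |
|---|---|---|
| 1% (assumed) | 28% | 38% |
| 1.5% (plan) | 15.1% | 23.1% |
| 2% (assumed) | 8% | 14% |
| 3% (assumed) | 2% | 5% |

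**No RAO among carriers of an unrelated yes/no predictor.** The overall rate is (0.11 + 0.015)/2 = 0.0625. For prevalence q (assumed) the chance is (1 − 0.0625q)^N:

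| Prevalence q | N=250 | N=194 |
|---|---|---|
| 5% | 46% | 54% |
| 10% | 21% | 30% |
| 20% | 4% | 9% |

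**At least one non-finite term, arm plus unrelated predictors.** Simulation with 4,000 trials per setting; prevalence 15% (assumed), with the results for 10% and 30% in brackets:

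| Model | N=250 | N=194 |
|---|---|---|
| Arm + 1 | 22% (34% to 15%) | 34% (46% to 24%) |
| Arm + 2 | 29% (45% to 16%) | 44% (59% to 26%) |

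Counting empty cells directly at 15% prevalence gave 22% and 35% with one predictor, and 30% and 43% with two. The two methods agree within simulation error.

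**Effect on the test of arm.** Exact enumeration, arm alone. Power is at 11% versus 1.5%; the false-positive rate is at 6.25% in both arms:

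| Test | Power, N=250 | Power, N=194 | False positives, N=250 | False positives, N=194 |
|---|---|---|---|---|
| Wald | 75.1% | 55.7% | 4.0% | 3.1% |
| Ordinary likelihood-ratio | 93.3% | 86.7% | 5.7% | 5.9% |
| Firth penalised likelihood-ratio | 91.9% | 82.4% | 4.7% | 4.5% |

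The direct chi-square comparison has power 91.9% and 82.7%. Among trials with no VASOBand RAO, Wald names arm in none, the ordinary likelihood-ratio test in at least 99.9%, and Firth in 99.9% (N=250) and 98.6% (N=194).

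**Worked case: RAO in 14/125 versus 0/125.**
- Chi-square: 250 × (14×125 − 0×111)² / (125 × 125 × 14 × 236) = 14.8, p = 0.0001.
- Ordinary fit: Wald p of 0.99 or higher, depending on where the iterations stop; ordinary likelihood-ratio p = 0.000007.
- Firth: with arm alone this amounts to adding one half to each cell, so the odds ratio is (0.5/125.5)/(14.5/111.5) = 0.031. The 95% profile interval is 0.0002 to 0.23 and p = 0.00003.

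**False positives for an unrelated predictor beside arm** (the simulated models above): ordinary likelihood-ratio 5.6–7.8% and Firth 3.1–4.8% at N=250; 3.8–6.9% and 3.1–4.4% at N=194.

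**Why the predictor list should be short** (1,500 simulated trials per setting, 15% prevalence). Beside arm, a real predictor with odds ratio 2 is detected in only 19–21% of trials at N=250 and 15–17% at N=194, whichever test is used. With arm plus eight predictors, seven of them unrelated, at least one false predictor is named in 46% (ordinary likelihood-ratio) or 24% (Firth) at N=250, and in 40% or 20% at N=194. Some term is non-finite in 55% and 72%. The plan does not propose eight predictors, but it does not rule them out.

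**The case against.** The plan does not say that arm is a term, and that the fit is ordinary is inferred from the absence of any penalised or exact method. The Wald p-value problem needs a second unstated choice, since a likelihood-ratio test restores the p-value for arm. The treatment question is answered by the chi-square test, and an empty cell would be visible in the table. The route that does not involve arm depends on prevalences the documents do not give. By the formula above, the chance at N=250 is 0.9% at 30% prevalence and 0.04% at 50%, and numeric predictors such as blood pressure have no such empty cell. Firth adds no information where events are few. Its false-positive advantage is also uneven: in a separate simulation of 8,000 trials with one unrelated predictor of 10% prevalence at N=194, the rates were 4.0% for the ordinary likelihood-ratio test and 3.6% for Firth. Naming the terms, testing by likelihood ratio and labelling the model exploratory would remove much of the harm within SPSS.

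Most of this stands, and it limits the severity. The power gap between Wald and Firth should not be credited to Firth, because the ordinary likelihood-ratio test closes it too. The cap of one or two predictors is a judgement. What remains is that a likelihood-ratio test repairs the p-value but not the estimate: the odds ratio and Wald interval are still not finite, and a predictor model is read for its odds ratios.

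**Conclusion.** The concern holds and is minor. Run as written on the plan's own rates, the model rests on about 16 events (12 at N=194). If arm is a term, it yields no finite odds ratio for arm in 15% of trials (23%). With one or two uncommon yes/no predictors added, the chance of at least one unusable term is 15–45% at N=250 and 24–59% at N=194 across the assumed prevalences of 10–30%.

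The arm figure depends on the 1.5% planning rate and equal allocation; the predictor figures depend on assumed prevalences. The Wald p-value problem arises only if Wald tests are used. The harm is confined to a supportive analysis: patent hemostasis and the direct comparison of RAO are unaffected.

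**What to change.** Replace the logistic regression sentence with text such as:

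> RAO 1 hour after device removal was modelled by Firth penalised logistic regression with randomised arm and one or two further predictors, named before the analysis from the recorded demographic, laboratory, procedural and post-procedural variables. Odds ratios are given with 95% profile penalised-likelihood confidence intervals and penalised likelihood-ratio p-values. Predictor results are exploratory.

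One predictor beside arm leaves 15.6/2 = 7.8 expected events per term at N=250 and 12.1/2 = 6.1 at N=194; two leave 5.2 and 4.0. If a chosen predictor is recorded after band application, report the arm-only model as well, because the band may affect that predictor.

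**Cost.** A short edit, a decision on the predictors, and possibly a penalised routine outside the standard logistic procedure of SPSS 26. Fewer candidates are examined. Against an ordinary likelihood-ratio test, power for arm falls by about 1 point at N=250 (93.3% to 91.9%) and 4 points at N=194 (86.7% to 82.4%), with a lower false-positive rate. Data collection, sample size and the primary analysis do not change.

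### Does using 80% patency for a well-trained site, but average RAO of 11% in the same TR Band arm, undermine the 250-patient calculation?

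*Combined protocol and SAP*

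**What the plan says.** Both calculations are in the Sample Size Calculation section of the combined protocol and SAP.

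- **Primary endpoint (patency at 15 minutes).** "We used an optimistic 80% patent hemostasis rate in the TR Band group", and the reason given is "in view of the high level of training of the research site in preventing RAO". The comparison is with a "95% rate of patent hemostasis in the dual-balloon band (VASOBand) group". The one earlier randomized trial that the plan relies on "has shown 96% achievement of patent hemostasis at 15 minutes after onset of compression", so 95% is slightly below the published figure. The result: "a Chi-square model provided a sample size of 194 patients equally divided between two groups", for 90% power at alpha .05.
- **Secondary endpoint (RAO).** The input is described as "Average incidence of RAO 1-hour after removal of" the device, drawn from recent trials. It "was expected to occur in 11% of patients in TR-Band group and 1.5% in the experimental group", which leads to 250 patients in total for 90% power at alpha .05. No adjustment for site training is mentioned.

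The plan does not derive either pair of rates from the other. Under Statistical Analysis it adds: "Mediation analysis was performed to identify potential mechanistic basis of the effect observed" in the VASOBand group. No mediator is named.

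**The concern.** The site's skill is described as skill in preventing RAO. It is used to set the patency rate, an intermediate outcome, but not visibly used for RAO itself. A reader would expect a site that prevents RAO well to have control-arm RAO below the average of other trials.

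The rates also seem not to fit together. If VASOBand prevents RAO by keeping the artery patent, one would expect the RAO contrast to be no larger than the contrast in non-patency. It is larger: 7.3-fold against 4-fold.

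At stake is the 90% power stated for RAO. If true control RAO is lower than 11%, or the true ratio is smaller, the RAO comparison is weaker than planned, and a non-significant result might be over-read as showing no effect.

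**Working it through.** **Inputs** (all from Sample Size Calculation): patency 80% vs 95%; RAO 11% vs 1.5%; totals 194 and 250; power 90%; alpha .05. Two-sided testing is assumed for both calculations, and equal allocation for the 250.

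**1. The plan's own figures.** With the unpooled formula, n per arm = (1.960 + 1.282)² × [p1(1−p1) + p2(1−p2)] / (p1−p2)².

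- Primary: 10.507 × (0.1600 + 0.0475) / 0.15² = 96.9, so 97 per arm and 194 in total. This matches the plan.
- RAO: 10.507 × (0.0979 + 0.0148) / 0.095² = 131.2, so 132 per arm and 264 in total. Other two-sided methods give 228 (arcsine), 234 (exact Pearson), 270 (pooled) and 310 (continuity-corrected). None gives exactly 250, but 250 lies within their range.
- RAO power at 125 per arm: 88.6% (unpooled), 87.8% (pooled), 91.9% (exact enumeration, uncorrected Pearson), 86.1% (Fisher). The stated 90% is fair for an uncorrected chi-square test.

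**2. The apparent mismatch.** Suppose RAO risk is a if the artery is not patent at 15 minutes and b if it is, with a and b the same in both arms:

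- TR Band: 0.20a + 0.80b = 0.11
- VASOBand: 0.05a + 0.95b = 0.015

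The solution is a = 61.7% and b = −1.7%, which is not a possible risk. Under this model the ratio is largest at b = 0, where it is 0.20/0.05 = 4, against 0.11/0.015 = 7.3. With the published 96% the limit is 0.20/0.04 = 5.

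**3. What the model would imply for power at 250** (exact Pearson):

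| RAO rates | Basis | Power |
|---|---|---|
| 11% vs 1.5% | as stated | 91.9% |
| 11% vs 2.75% | 4-fold, control rate held | 76.1% |
| 6% vs 1.5% | 4-fold, VASOBand rate held | 45.9% |
| 11% vs 2.2% | 5-fold, control rate held | 83.9% |
| 7.5% vs 1.5% | 5-fold, VASOBand rate held | 65.2% |

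Only the first row uses rates found in the documents.

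**4. Is the model the plan's?** It needs two things: RAO depends on one binary reading at 15 minutes, and patients with the same reading carry the same RAO risk in both arms. The plan's procedures point the other way:

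- Under Hemostasis protocol, the ulnar balloon stays inflated for 60 minutes, so treatment still differs between arms for 60 − 15 = 45 minutes after the reading.
- Pressure adjustment is allowed throughout in Group 1. In Group 2 it is limited to the 60-minute point and to correcting inadequate hemostasis.
- Under Evaluation of radial artery patency, patency is read again at 60, 90 and 120 minutes. The difference between arms could be larger later than at 15 minutes.

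Without the equal-risk assumption the four rates can hold together. At b = 0, TR Band risk in non-patent patients is 0.11/0.20 = 55%. VASOBand's patency mix would then give 0.05 × 55% = 2.75%. Reaching 1.5% needs a residual ratio of 1.5/2.75 = 0.545, an average further reduction of about 45% beyond 15-minute patency, and more if b is above zero. The plan does not claim such an effect, but nothing in it rules one out.

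**5. Direction of the patency inputs.** Calling 80% optimistic for the control arm, and using 95% where 96% was published, both narrow the primary contrast and so raise the primary sample size. Setting a deliberately narrowed patency contrast beside an RAO contrast taken from the literature will tend to show a gap of this kind. On the model in step 2, 11% vs 1.5% fits TR Band patency of up to 1 − 0.05 × 7.33 = 63%, or 71% with 96% in the VASOBand arm.

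**The case for a change.** The strongest case for acting needs no model. The same site's training is invoked for one TR Band input and is silent for the other, although it is training against the very outcome left unadjusted. The margin is thin: with VASOBand at 1.5%, exact Pearson power is below 90% once control RAO is under 10.6% and below 80% once it is under 9.0%, and the training argument points in that direction. The larger total of 250 rests only on the RAO calculation. A few sentences would clear the matter up.

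The asymmetry is real and the sensitivity figures are right. They do not show an error. Any power calculation weakens when control risk is lower than planned, and the plan states the rates on which its 90% depends. Whether 11% already reflects experienced sites cannot be judged, because the plan does not describe the trials behind it and gives no unadjusted patency rate. The lower powers of 76% and 46% use RAO rates that appear nowhere in the documents, so writing them into the SAP would add unsourced scenarios. Reporting the RAO difference with a confidence interval is good practice whatever the planning rates were, so it does not turn on this point.

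**Conclusion.** The concern does not call for a change. The 250 is adequate for its stated rates: 91.9% power by exact Pearson, and 86% to 92% across the methods tried, assuming a two-sided test and 125 per arm. TR Band patency of 80% and RAO of 11% can coexist in one arm. The claim that the RAO ratio cannot exceed 4 rests on an added assumption, that RAO acts only through 15-minute patency with equal risks in both arms, which the plan neither makes nor makes plausible.

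What stands is a small gap in explanation: the plan does not say why training bears on patency and not on RAO. Filling it would alter no conduct, analysis or result. The primary calculation is untouched (194 reproduced; 96.4% power at 250). A reader who meets a non-significant RAO result should keep in mind that the 90% belongs to 11% vs 1.5% and falls quickly below about 10% in the control arm.
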